**C.4.9 Task Practice and Mock MRI Simulation:** Prior to the real MRI scan, the subjects undergo at least 10 min of practice of the fMRI tasks until it is clear that the procedures are understood and that the majority of the practice responses are correct. After that, the subjects undergo a mock MRI scan using a Philips product MRI

Simulator. Lying in the mock scanner, the subject performs the fMRI tasks as in the real scan, while listening to a recording of MRI sounds. The fMRI tasks are written in E-Prime 1.2 (Psychology Software Tools).

**C.4.10 Pre-scan Screening:** Immediately prior to the real MRI scan, all subjects undergo urine drug screen and breath alcohol screen. Female subjects also undergo urine pregnancy screen. The subjects with a breath alcohol result of greater-than-zero do not proceed for the MRI scan that day, and are rescheduled. The control subjects with a positive urine drug screen are excluded from the study. The female subjects with a positive urine pregnancy test are excluded from the study. Subjects who regularly smoke tobacco are asked to smoke two hours prior to the first fMRI scan, and not to smoke after that until the fMRI scans are finished.

**C.4.11 MRI Scans:** The MRI session is approximately 90 min, with a 10 min break in the middle. The first 2 series are a T1-weighted spin echo 3-plane localizer (scout), and a SENSE localizer. A high resolution T1-weighted 3D-MPRAGE series is acquired with the following parameters: 256 x 256 acquisition and reconstruction matrix, in-plane resolution= 0.94 mm, 170 sagittal slices, 0.94 slice thickness. This is followed by 3 working memory (IMT/DMT) **and 3 response inhibition (Go-NoGo) fMRI series (runs)** with approximately 2 minutes rest between runs. Each fMRI series is a single shot spin-echo echoplanar (EPI) pulse sequence (see next section for rationale), with SENSE factor= 2.0, repetition time= 2212 ms for IMT/DMT **and 2500 ms for Go-NoGo**, echo time= 75 ms (optimized for spin echo), flip angle= 90 degrees, number of axial slices = 22 for IMT/DMT **and 25 for Go-NoGo**, field-of-view= 240 mm x 240 mm, in-plane resolution 3.75 mm x 3.75 mm, slice thickness= 3.75 mm, gap= 1.25 mm, repetitions= 294 for IMT/DMT **and 256 for Go-NoGo** after 10 dummy acquisitions, total duration = 10 min 47 s for IMT/DMT **and 10 min 40 s for Go-NoGo**. A 3D-FLAIR and T2-weighted fast spin echo are acquired to rule out incidental intracranial findings.

**C.4.12 Spin-Echo EPI:** Spin-echo EPI, rather than gradient-echo EPI, is used for fMRI in this study to avoid signal losses caused by through-slice dephasing in regions that are affected by strong susceptibility gradients at 3 T [168-170]. The regions affected by strong susceptibility gradients near air-tissue interfaces include medial orbitofrontal cortex and medial temporal areas that are important for drug addiction research. In addition to its advantage of eliminating signal dropout, spin-echo EPI has other advantages over gradient-echo EPI including greater extravascular signal component, less spatial distortion, and more specific spatial localization at 3T [169, 171]. Although the magnitude of the BOLD effect is somewhat lower in spin echo EPI compared to gradient echo EPI at 3T (in areas of the brain that are not affected by susceptibility dropout), a cognitive fMRI study using spin-echo EPI at 3T [169] found significant activation in the same cortical areas that were found using gradient echo EPI (i.e., in the areas not affected by susceptibility dropout). Importantly, that study found significant activation in predicted medial orbitofrontal areas that were not found with gradient echo EPI [169]. Likewise, our fMRI [35] and fMRI-based DCM [138] studies, which used the same working memory task and scanning parameters as in the proposed project, found significant findings in medial orbitofrontal cortex, as well as in expected cortical areas that are not affected by magnetic susceptibility dropout.

**C.4.13 fMRI presentation system:** Stimulus presentation and recording of behavioral performance during fMRI scanning is managed through the Eloquence fMRI System (Invivo Corporation, Orlando, Florida), an update of the Integrated Functional Imaging System-Stand Alone system (IFIS-SA, InVivo Corporation, Orlando, Florida). The subject views the task on an LCD video display unit that is built into the head coil. The subject responds to the task by pressing a keyboard-like button with the right index finger.

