C.3.1 Participants and Recruitment for the Clinical Trial: Male and female treatment-seeking individuals, 18 to 55 years old, who meet current OSM-IV criteria for cocaine dependence and report using cocaine within the past 30 days are enrolled. Eligible subjects are required to submit at least one positive urine toxicology screen for the cocaine metabolite benzoylecgonine (BE)  $> 300$  ng/ml, during the one-week screening and pretreatment assessment period. Subjects currently dependent on any psychoactive substance other than cocaine, nicotine, or marijuana are excluded. 60 treatment-seeking COs will be recruited.

C.3.2 Screening, Pretreatment, Randomization for the Clinical Trial: Candidates signing written informed consent enter a one-weiintake and assessment phase to evaluate eligibility and administer baseline pretreatment measures. Those who fail to return for required visits during this period are not randomized to treatment so as to reduce early treatment dropout rates [152]. An *urn randomization [153] procedure assigns subjects to one of the four treatment groups.* This procedure balances groups on pretreatment characteristics that may influence measures of cognitive performance and/or treatment outcome. The variables include (a) severity of cocaine use, based on days using cocaine in past 30 days and KMSK score [151]; (b) lifetime duration of cocaine use; (c) level of marijuana use, based on days using in past 30 days; (d) Barratt Impulsiveness Scale (BIS) [202], measuring trait impulsivity.

*In the Clinical Trial, there is one active medication arm and one placebo arm.* Equal allocation to treatment conditions is expected, as follows: 30 COs assigned levodopa/carbidopa 400/100 BID, and 30 COs

assigned placebo. Treatment assignment is concealed to all staff, including the investigators. Only the study pharmacist who dispenses the study medications is unblinded to participants' assigned condition. At each clinic visit (Monday, Wednesday, Friday) subjects are administered the medication at the dispensing window and given take-home doses for intervening days.

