**C.3.6 Assessment of Medication Compliance:** Riboflavin (50 mg) is added to the medication (and placebo) capsules and used as a marker to monitor compliance. The compliance to the treatment regimens is assessed by pill-counting and by urine riboflavin determination.

**C.4 Experimental Design and Methods for the snDCM Study:** **C.4.1 Subjects for the snDCM Study:** There are 3 groups in the snDCM study: (a) medication group, (b) placebo group, and (c) control group. Conservatively estimating approximately 20% unusable scans in each group because of excessive head motion, clinical structural abnormalities, artifacts, or subject no-show for the scan, this project will need to recruit a total of 30 treatment-seeking CDs for the medication group (15 male and 15 female), 30 treatment-seeking CDs for placebo group (15 male and 15 female), and 30 age-, handedness-, and education-matched non-drug-using healthy control subjects (15 male and 15 female) in order to achieve 24 subjects per group for final analysis (Power Analysis section C.4.21). Thus, we need to recruit 24 subjects each year over the first 3 years and 18 subjects during Year 4. Fewer subjects will be recruited during Year 4 because more time in Year 4 will be devoted to final data analysis, write-up, presentation of findings, and subsequent grant applications.

**C.4.2 Subject Recruitment and Screening:** The medication group will consist of 30 subjects assigned to levodopa/carbidopa. The placebo group will consist of 30 subjects assigned to placebo in the clinical trial. The 30 non-drug-using healthy control subjects (control group) will be recruited through advertising in local newspapers and word of mouth. Written informed consent form will be obtained from all subjects.

All control subjects undergo an initial screening that consists of a physical examination, routine blood work, urinalysis, electrocardiogram (EKG), metal screening, structured diagnostic interview (SCID), addiction severity index (ASI), and human immunodeficiency virus (HIV) screening. We anticipate screening 45 potential control subjects in order to recruit 30 control subjects (yielding 24 control subjects in the final analysis).

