**C.4.3 Subject inclusion/exclusion criteria:** The patients who meet DSM-IV criteria for current cocaine dependence, have at least 1 positive urine benzoylecgonine (BE) specimen ( $> 300$  ng/ml) during intake, and are assigned medications or placebo, will be the candidates for this study. In addition, the included subjects must simultaneously meet the following criteria: (a) Be between 18 and 50 years of age; (b) Right handed; (c) Have no past history of Psychiatric or non-Psychiatric medical disorders which could affect the central nervous system as assessed by SCID and physical examination; (d) Be in acceptable health on the basis of interview,

medical history, labs, and physical exam; (e) Be able to understand the consent form and provide written informed consent; (f) Have no metal fragments or other bodily metal (e.g., pacemaker) or significant claustrophobia that would put the subjects at risk for MRI scanning. (For a complete list of inclusion and exclusion criteria see Human Subjects section below).

**C.4.4 Coordination between the Proposed Study and the Clinical Trial:** For eacCD, the MRI session will be conducted in Week 1, which is before the treatment is initialized (baseline pretreatment). The treatment outcome (see Section C.3.4 Treatment Outcome) will be shared for the snDCM study.

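### The trial and imaging eligibility criteria differ while the same 60 patients are counted for both, so 24 usable scans per arm is met only if no randomised patient fails the imaging criteria

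*Protocol*

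**What the plan says.** The clinical-trial part of the protocol (C.3.1) enrols "Male and female treatment-seeking individuals, 18 to 55 years old" and states that "60 treatment-seeking COs will be recruited". It gives no handedness or MRI-safety criterion. C.3.2 splits the 60 equally, 30 to each arm.

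The imaging part uses the same patients. C.4.2 states "The medication group will consist of 30 subjects assigned to levodopa/carbidopa" and "The placebo group will consist of 30 subjects assigned to placebo in the clinical trial". The recruitment and consent section (2.a) likewise draws imaging subjects from the trial's participants.

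C.4.3 takes patients assigned to medication or placebo as the candidates and adds further conditions. They must "Be between 18 and 50 years of age", be right-handed, and have no bodily metal or significant claustrophobia. The numbered eligibility list after C.4.22 repeats these conditions.

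C.4.1 derives the recruitment number: "Conservatively estimating approximately 20% unusable scans in each group because of excessive head motion, clinical structural abnormalities, artifacts, or subject no-show", so that 30 recruited per group become 24 analysed. C.4.21 bases the Aim 2 correlation power of 86% on 24 subjects.

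**The concern.** Two eligibility definitions apply to one set of 60 patients. A patient aged 51 to 55 can be randomised under C.3.1 but cannot be imaged under C.4.3. The same holds for a patient who is left-handed or cannot safely be scanned, since C.3.1 does not screen for either. Such a patient is still counted among the 30 in that arm's imaging group.

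Nothing in the sample-size argument absorbs this loss. The four causes listed in the 20% allowance are head motion, structural abnormality, artifact and no-show. For controls the protocol does plan for screening loss (45 screened to recruit 30, C.4.2). It has no such step between randomised and imaged patients.

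At stake are the 24 per arm and the Aim 2 power that rests on it. C.4.20 already describes the treatment-by-gating interaction, the key term for Aim 2, as probably underpowered, so Aim 2 has little room for further loss.

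**Working it through.** **Inputs from the protocol.** 60 patients, 30 per arm (C.3.1, C.3.2); imaging groups of 30 and 30 (C.4.2); 20% unusable and a target of 24 (C.4.1); effect size 0.60 for the correlation, two-sided alpha 0.05, n = 24, power 86% (C.4.21); Aim 1 d = 1.89, 24 per group, power 99.9% (C.4.21).

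**Input not in the documents.** The share q of randomised patients who fail the imaging criteria. It is an assumption here, shown from 0% to 20%.

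**Step 1: the plan's own figures.**
- 24 / (1 - 0.20) = 30, and 30 x 0.80 = 24.0. The recruitment number reproduces exactly, with nothing to spare.
- The recruitment schedule in C.4.1 gives 24 x 3 + 18 = 90 = 60 patients + 30 controls. It contains no reserve patients.
- Aim 2 power by Fisher z is Phi(atanh(0.60) x sqrt(n - 3) - 1.96). At n = 24 this is 88.8%. With the Spearman variance, 1.06/(n - 3), it is 87.0%, closer to the stated 86%. The pilot in C.2.4 used Spearman.

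**Step 2: allow for ineligible patients.** Expected usable n per arm = 30 x (1 - q) x 0.80. Randomised per arm needed to keep 24 = 24 / (0.80 x (1 - q)), rounded up.

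| Assumed q | Expected usable n per arm | Fisher z power at that n | Fisher z power, n rounded down | Spearman-variance power, n rounded down | Randomised per arm to keep 24 |
|---|---|---|---|---|---|
| 0% | 24.0 | 88.8% | 88.8% (24) | 87.0% (24) | 30 |
| 5% | 22.8 | 87.0% | 85.6% (22) | 83.5% (22) | 32 |
| 10% | 21.6 | 84.8% | 83.7% (21) | 81.5% (21) | 34 |
| 15% | 20.4 | 82.4% | 81.5% (20) | 79.3% (20) | 36 |
| 20% | 19.2 | 79.7% | 79.2% (19) | 76.8% (19) | 38 |

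Example at q = 10%: 30 x 0.90 x 0.80 = 21.6, and Phi(0.6931 x sqrt(18.6) - 1.96) = Phi(1.03) = 84.8%.

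**Step 3: Aim 1.** With d = 1.89, power for the two-group comparison is still about 99.99% at 18 per group, so this issue does not touch it.

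**The case against.** **The 30 may already mean eligible recruits.** C.4.1 sets a recruitment target for the imaging study, and C.4.3 defines who may enter that study. If the 30 are MRI-eligible recruits, 30 x 0.80 = 24 stands. But this does not fit the rest of the protocol. C.3.1 and C.3.2 recruit 60 in total and assign 30 to each arm, C.4.2 makes those same 30 and 30 the imaging groups, and the 90-subject schedule has no spare patients. The reading works only if all 60 are in practice recruited to the imaging criteria. The protocol does not say so, and its trial age range says otherwise.

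**Much of the screening is already early.** C.3.2 has a one-week intake before randomisation. C.4.14 puts metal screening on Day 1, the mock scan on Day 2 and the MRI on Day 3, and C.4.4 puts the MRI before treatment starts. This stands, and it makes the repair easy. What is missing is a statement that candidates who fail the imaging criteria are not randomised.

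**The loss of power is modest.** This also stands. By Fisher z at the expected n, power stays above the stated 86% at 5% ineligible and reaches about 80% only at 20%. The one-arm correlation is also not the analysis that C.4.20 calls critical. The interaction is, and the plan already concedes that its power is low.

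**Bias.** A reader might infer that imaging only some of those assigned biases the comparison of arms. The documents do not support that. Age, handedness, metal and claustrophobia are baseline traits, the scan precedes treatment (C.4.4), and assignment is concealed from all staff except the dispensing pharmacist (C.3.2). The cost is in precision and generalisability.

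**Conclusion.** The inconsistency is real and can be verified in the text. The age ranges differ, right-handedness and MRI safety appear only in the imaging criteria, the same 60 patients serve both parts, and the attrition allowance is used up before any ineligible patient is counted. The expected number of usable scans is therefore 24 per arm only if the ineligible share is zero.

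A reader might go further and conclude that 24 will not be reached, or that the trial accepts any handedness. Neither is established. The ineligible share is not given and could be zero in practice, and C.3.1 is silent on handedness rather than permissive.

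The size is moderate and rests on the assumed share. Between 5% and 20% ineligible, expected usable n per arm is 22.8 to 19.2, and Fisher z power for the one-arm correlation is about 87% to 80%. With the Spearman variance and n rounded down, power falls just below 80% at 15% ineligible. These figures also assume that the 20% scan loss applies equally to the patients who remain and that the true correlation is 0.60. Aim 1 is essentially unaffected.

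**What to change.** Reconcile C.3.1 with C.4.3 and the numbered eligibility list. State that one set of criteria (age range, handedness, MRI safety) is checked during the one-week intake, before urn assignment, so that all 60 randomised patients are eligible for imaging. The claustrophobia check belongs in that same period if the mock scan is to inform it. The cost is a short eligibility amendment and a somewhat smaller recruitment pool. The documents give no figure for how much smaller, and more candidates may need to be screened. No extra randomised patients are needed.

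If the two sets of criteria are kept, add MRI ineligibility to the allowance in C.4.1 with a stated assumed share, and restate the expected usable number per arm and the Aim 2 power in C.4.21. This costs only text. Keeping 24 usable per arm under split criteria would instead need about 32, 34, 36 or 38 randomised per arm at 5%, 10%, 15% or 20% ineligible.

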**C.3.3 Treatment for the Clinical Trial:** During the 12-week active trial participants are scheduled to attend 3 clinic visits per week (Monday, Wednesday, and Friday). Weekly cognitive behavioral therapy (CBT), an evidenced-based psychosocial treatment for cocaine dependence, is used as the behavioral therapy platform. Participants receive individual cognitive behavioral therapy in 50-minute weekly sessions. The CBT is based on the model of relapse proposed by Marlatt and Gordon [154].

**C.3.4 Treatment Outcome:** The primary outcome measure of cocaine use/nonuse is based on *urine drug screen* levels (acquired 3 x per week) of the cocaine metabolite benzoylecgonine (BE), coded as "positive" for cocaine use if BE  $\geq 300$  ng/ml. However, urine-based definitions of cocaine use/nonuse have limitations in terms of data loss (due to missed visits) and carryover effect. Recent procedures for combining self-report and urine BE have been recommended [159, 160]. Thus, as a secondary measure of cocaine use/nonuse, the new SRPHK1 (SelfReportPHarmacoKinetic1) coding method is used. This classifies daily cocaine use based on evaluation of self-report (SUR) (obtained 3 x per week), quantitative urine BE levels, and participants' concordance rate (agreement between self-report and urine result). Retention in treatment is measured in two ways: (a) As a binary variable, defined as "completing" 12 weeks of cognitive behavioral treatment, since this cutoff is regarded as standard duration of treatment [161] and predictive of better outcome [162]. (b) A secondary continuous measure of retention is the total number of weeks a subject remained in treatment.

**C.3.5 Retention of Participants:** As part of participation in the clinical trial, participants receive incentives for attending the in-person intake (\$50.00 in gift cards) and end of study (\$50.00 in gift cards). They also receive \$5 for each medication pack returned and bus/parking tokens as needed to help defray the costs of travel. Also during treatment, for each visit attended, subjects earn a draw from the attendance voucher "fishbowl", with prizes ranging in value from \$0 to \$100 (one slip). Prizes are exchanged for vouchers. In addition, they receive approximately \$50.00 in gift cards for completing behavioral/cognitive laboratory assessments. All parking is free. Subjects receive an additional \$130 for completion of the MRI scans.

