**C.4.6 Response Inhibition Task for fMRI:** An event-related Go/NoGo task [1] is used for fMRI of response inhibition. In each run, the subjects look at a total of 224 visual stimuli that are sequentially presented in random order. Each stimulus is displayed for 500 ms, and any two neighbor stimuli are separated by a blank screen lasting 1900, 2100, or 2300 ms (uttered randomly). Each visual stimulus consists of lines enclosed within two boxes that are presented simultaneously side by side. The subjects are instructed to look at both boxes and to discriminate the direction of the lines. The subjects are instructed to press a button using their right index finger only when they see that both boxes show diagonal lines in the same direction in both boxes (Go trials). The subjects are instructed not to press any button when they see that both boxes show horizontal lines (easy-NoGo trials), or when they see that one box contains diagonal lines that are in the opposite direction of the diagonal lines in the other box (hard-NoGo trials). For Go trials, a correct response is defined as a key-press completed within 600 ms. For NoGo trials, an incorrect response is defined as a key-press completed within 600 ms. There are 168 Go trials (75%), 28 easy-NoGo trials (12.5%), and 28 Hard-NoGo trials (12.5%) in each fMRI run (10 min 40 s per run). For detailed descriptor, please see reference [1].

**C.4.7 Pre- and Post-treatment Behavioral Performance:** Because fMRI sessions in this project are conducted only during pretreatment baseline, this project will also acquire out-of-scanner pre-treatment and post-treatment (week 12) behavioral data for the cognitive tasks. Pre-treatment performance will be considered as a possible confounding factor and will be controlled as a covariate in the statistical analysis (Section C.4.20). Post-treatment behavioral performance is a treatment outcome and will be included in the treatment prediction analysis (C.4.20). In addition, [name], who is an expert in the behavioral science of drug addiction, will be a Consultant on this project to advise on the behavioral data implementation and analysis.

**C.4.8 MRI Scanning Site and Devices:** MRI sessions are conducted at the Magnetic Resonance Imaging Center of the UTHSC-H, using a research-dedicated Philips Intera 3.0 T MRI scanner with an 8-channel receive head coil (Philips Medical Systems, Best, Netherlands).

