Urn randomization [153], a form of stratified randomization, will help ensure comparability of treatment groups on baseline severity and duration of cocaine abuse. Pretreatment task behavioral performance or demographic variables on which group differences are detected, and which are correlated with outcomes, meet the definition of confounders [192, 193]. In such cases, analyses will evaluate the robustness of findings after statistically controlling for the confounder. If conclusions remain unchanged after covarying for the confounder, the more parsimonious model will be reported along with a statement indicating its robustness to covariation for potential confounding. If inclusion of the covariate alters the conclusions of the analysis, both models will be reported. Treatment success is a function of two elements: (a) retention and (b) demonstrating cocaine-free status using the SRPHK1 criteria (see section C.3.4). The Treatment Effectiveness Score (TES) provides a metric for this composite outcome [194]. TES is the sum of all cocaine-negative tests (according to SRPHK1 rules). Higher TES indicates that participants both continue to participate in the study and are negative for cocaine. For each group, BMA (section C.4.19.4) is conducted across all OCMs in the model space. Group difference in the gating effect by the dorsal striatum is assessed using Bayesian confidence probability [195]. In addition, BMA is conducted across all OCMs in the model space for each subject in the medication group and in the placebo group. Evaluation of differential treatment response, measured by the TES, as a function of the averaged (across the OCM model space) gating effect, will use Poisson regression. Violations of assumptions of dispersion will result in the use of more appropriate approaches such as zero-inflated Poisson, negative binomial, or zero-inflated negative binomial models. Regression of treatment, averaged gating, and their interaction will permit evaluation of differential treatment response as function of gating. The critical element in doing so is the evaluation of the interaction term. Given that the current study is powered to detect group differences, it is likely underpowered to detect an interaction. Brookes, et al. [196] demonstrate that for studies with 80% power to detect a between-groups effect, power to detect an interaction effect of the same magnitude as the main effect is approximately 29%. One solution is to adopt a Bayesian subgroup analysis approach [197-201]. This approach utilizes the posterior distribution of the interaction parameter to estimate the

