Urn randomization, a form of stratified randomization, will help ensure comparability of treatment groups on baseline severity and duration of cocaine abuse. Pretreatment task behavioral performance or demographic variables on which group differences are detected, and which are correlated with outcomes, meet the definition of confounders. In such cases, analyses will evaluate the robustness of findings after statistically controlling for the confounder. If conclusions remain unchanged after covarying for the confounder, the more parsimonious model will be reported along with a statement indicating its robustness to covariation for potential confounding. If inclusion of the covariate alters the conclusions of the analysis, both models will be reported. Treatment success is a function of two elements: (a) retention and (b) demonstrating cocaine-free status using the SRPHK1 criteria. The Treatment Effectiveness Score (TES) provides a metric for this composite outcome. TES is the sum of all cocaine-negative tests (according to SRPHK1 rules). Higher TES indicates that participants both continue to participate in the study and are negative for cocaine. For each group, BMA is conducted across all DCMs in the model space. Group difference in the gating effect by the dorsal striatum is assessed using Bayesian confidence probability. In addition, BMA is conducted across all DCMs in the model space for each subject in the medication group and in the placebo group. Evaluation of differential treatment response, measured by the TES, as a function of the averaged (across the DCM model space) gating effect, will use Poisson regression. Violations of assumptions of dispersion will result in the use of more appropriate approaches such as zero-inflated Poisson, negative binomial, or zero-inflated negative binomial models. Regression of treatment, averaged gating, and their interaction will permit evaluation of differential treatment response as function of gating. The critical element in doing so is the evaluation of the interaction term. Given that the current study is powered to detect group differences, it is likely underpowered to detect an interaction. Brookes, et al. demonstrate that for studies with 80% power to detect a between-groups effect, power to detect an interaction effect of the same magnitude as the main effect is approximately 29%. One solution is to adopt a Bayesian subgroup analysis approach. This approach utilizes the posterior distribution of the interaction parameter to estimate the probability that it exceeds some number (e.g., for Poisson regression a Risk Ratio of 1.0). Specification of vague neutral priors will reflect uncertainty regarding parameter values, utilizing prior distributions for the lower order effects that are neutral and diffuse with specification  $\sim N(0, 1 \times 10^{-6})$  on the log scale (i.e., centered at the null hypothesis with a 95% Credible Interval of  $\pm 1960$ ) for all coefficients, and  $\sim U(0, 100)$  for any required dispersion terms. Examination of the interaction of treatment and the subgroup index forms the crux of the evaluation of the subgroup effect. For evaluating the interaction representing the differential subgroup effect, analysis will be conducted in two ways: (a) utilizing diffuse, indifferent priors ( $\sim N(0, 1 \times 10^{-6})$ ) on the log scale for the interaction coefficients, and (b) using informative skeptical priors for the coefficients will evaluate sensitivity of statistical conclusions to specification of priors. Informative, skeptical priors will be derived via the method first proposed by Dixon and Simon. Evaluation of resulting posterior distributions will permit conclusions regarding the probability that subgroup/interaction effects of varying magnitudes obtain. Examples of this use of the posterior distribution may be found in Green et al. (2009). Bayesian modeling will use SAS v9.2 (Proc Genmod and Proc Monte-Carlo Markov chain [MCMC]), and in WinBugs 1.4.3 (<http://www.mrc-bsu.cam.ac.uk/bugs>). Convergence of Bayesian analyses on the posterior distributions via MCMC will be assessed via graphical (Trace Plot, Autocorrelation Plot) and quantitative (Geweke Diagnostics, Gelman-Rubin Diagnostics, and Heidelberger-Welsh Diagnostics) evidence. Evaluation of posterior distributions will permit statements regarding the probability that effects of varying magnitudes exist, given the data.

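### Post-treatment task performance is an outcome tested only at week 12, with no test planned for patients who leave earlier, so its relation to gating would rest mainly on completers

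*Protocol*

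**What the plan says.** Protocol C.4.7 notes that scanning is done only before treatment, so "this project will also acquire out-of-scanner pre-treatment and post-treatment (week 12) behavioral data for the cognitive tasks". It gives the later measurement the status of an outcome: "Post-treatment behavioral performance is a treatment outcome and will be included in the treatment prediction analysis (C.4.20"). It also says that pre-treatment performance will be a covariate.

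C.3.4 lists retention among the treatment outcomes: "Retention in treatment is measured in two ways". The first measure is binary, completion of 12 weeks of behavioural treatment. The other is continuous: "A secondary continuous measure of retention is the total number of weeks a subject remained in treatment".

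C.4.20 makes retention part of the composite: "Treatment success is a function of two elements: (a) retention and (b) demonstrating cocaine-free status using the SRPHK1 criteria". It adds: "Higher TES indicates that participants both continue to participate in the study and are negative for cocaine".

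The only response model written out, in C.4.20 and again in the SAP, is for that composite: "Evaluation of differential treatment response, measured by the TES". Neither document gives a model, an analysis set or a missing-data method for week-12 task performance. The 20% allowance in C.4.1 covers unusable scans and missed scans, not treatment dropout. C.3.2 shows that dropout is expected, since candidates who miss intake visits are not randomised in order to reduce it, but no rate is given.

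**The concern.** The single post-treatment test falls at the time that separates completers from dropouts. A patient who leaves in week 5 still has a TES, because negative tests are summed and later ones simply do not accrue. The same patient has no post-treatment task score unless somebody brings them back at week 12, and nothing in the plan says that this will happen.

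Two things are at stake. The first is precision: the power statement in C.4.21 assumes an outcome for all 24 subjects. The second is bias. Aim 2 expects pretreatment gating to predict treatment response, and retention is one element of how response is scored. If retention depends on gating and also on cognition, then restricting the analysis to those who stayed can create, hide or change a gating-performance relation. A score not taken when the patient leaves cannot be recovered later, so the matter has to be settled in the protocol and not at analysis.

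**Working it through.** **Inputs from the documents.** Correlation 0.60, two-sided alpha 0.05, n = 24, stated power 86% (C.4.21). Thirty recruited per group, 20% scan loss (C.4.1): 30 × 0.80 = 24. The power statement concerns gating and treatment outcome in general; none is given for task performance, so it is borrowed here as the nearest figure.

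**Reproducing the stated power.** Power = Φ(atanh(r) × √((n − 3)/v) − 1.96), with atanh(0.60) = 0.693.
- Pearson, v = 1: 0.693 × √21 = 3.176; Φ(1.216) = 88.8%.
- Spearman, the method of the pilot, v = 1.06: 87.0%. Simulated Spearman: 84.9%.

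The stated 86% therefore reproduces to within two points on the Spearman basis, with an outcome for all 24.

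**Loss of precision.** Retention is an assumed range. The number with a score is 24 × retention, rounded down.

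| Retained | n | Fisher-z power, r = 0.60 | Simulated Spearman |
|---|---|---|---|
| 100% | 24 | 89% | 85% |
| 80% | 19 | 79% | 75% |
| 70% | 16 | 71% | 65% |
| 60% | 14 | 63% | 58% |
| 50% | 12 | 55% | 50% |

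For example, at n = 12: 0.693 × √9 = 2.079; Φ(0.119) = 55%.

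**Selection bias.** Assume no true gating-performance relation. Let a latent retention score with unit variance correlate a with gating and b with performance, and let the top fraction p be retained. With c the cut-off, λ = φ(c)/p and δ = λ(λ − c), the correlation among completers is

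−abδ / √[(1 − a²δ)(1 − b²δ)].

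Assumed ranges: a from −0.3 to −0.6, b from 0.3 to 0.5, p from 40% to 70%.
- Mildest, p = 70%, a = −0.3, b = 0.3: c = −0.524, λ = 0.497, δ = 0.507. Result: 0.0456/0.954 = 0.048.
- Strongest, p = 40%, a = −0.6, b = 0.5: c = 0.253, λ = 0.966, δ = 0.688. Result: 0.2065/√(0.752 × 0.828) = 0.26.

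**Direction.** The sign follows the assumed signs. A separate simulation used logistic retention at 60%, with a log-odds slope of 1 per SD. With no true relation it gave about −0.14 when retention rose with both variables and +0.14 when they acted in opposite directions. With a true correlation of 0.60, completers showed 0.47 and 0.65 respectively, and 0.57 when retention depended on only one of the two.

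**Would weighting cure it?** Inverse-probability weights built on gating were tried in the latent-retention setting. They moved the spurious correlation from 0.048 to 0.051 in the mildest case, and from 0.208 to 0.249 at a = −0.5, b = 0.5, p = 40%. They do not help, because retention there also depends on the performance score itself.

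**The case against.** The strongest reply concerns scope. A reader might infer that the trial's prediction analysis as a whole is conditioned on retention. The documents do not support that: the only prediction model written out uses TES, in which a dropout keeps a lower score. What is affected is an additional outcome that C.4.7 sends to C.4.20 and that C.4.20 never takes up.

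A reader might also infer that leavers are excluded from testing. That too goes beyond the text. C.4.7 fixes a time, not an attendance condition, and no completers analysis is announced. C.3.5 pays for an end-of-study visit and, separately, for behavioural and cognitive assessments, so a route to a week-12 test exists. What stands is that no test is planned for leavers and nothing says how missing scores will be handled.

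A third tempting inference comes from C.4.4: "the MRI session will be conducted in Week 1, which is before the treatment is initialized". On that numbering, week 12 would fall a week before a 12-week treatment ends. But C.4.7 itself calls the test post-treatment, and C.3.3 describes a 12-week active trial, so the end of treatment week 12 is the natural reading. Nor does the absence of a week-12 row from C.4.14 show that the test is unscheduled: that table covers screening to scan day and omits the treatment visits as well.

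Finally, the bias is modest beside sampling error. With 10 to 17 patients per arm (40-70% of 24), the Fisher-z standard error is 1/√(n − 3), about 0.38 to 0.27, which exceeds the computed bias. This is fair: lost precision is the firmer harm, and the bias figures rest wholly on assumed inputs.

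**Conclusion.** The point holds for week-12 task performance only and is best classed as a cheap improvement. Followed as written, the plan loses this outcome for every dropout who does not attend at week 12, and its relation to gating would be estimated mainly in completers.

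The size depends on a dropout rate that the documents do not give. With 50-80% of 24 retained, power at r = 0.60 falls from 89% to about 55-79%. With no true relation and the assumed correlations at 40-70% retention, the spurious completer correlation is about 0.05 to 0.26; other assumptions reverse its sign, so the direction is not known in advance. The TES analysis does not share this problem.

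**What to change.** In C.4.7, give the out-of-scanner task to every randomised patient at the end of treatment week 12, whether or not they still attend treatment, using the existing end-of-study visit and payment. For a patient known to be leaving early, also give it at the last attended visit.

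In C.4.20 and the SAP:
- write out the model for this outcome, in all randomised patients with a post-treatment value, adjusted for the pretreatment score;
- report missingness by arm and by gating;
- add a sensitivity analysis for informative missingness;
- label any completers-only result as such.

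Inverse-probability weights based on gating should not be relied on as the remedy.

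The cost is a short amendment using the same task and the existing visit and payment. The downside is that some dropouts will not return and early-exit tests will fall at varying times, so missingness will be reduced but not removed.
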